# 1.01.0 PROTOCOL SUMMARY AND/OR SCHEMA

Protocol title:	Phase II trial of Nintedanib in patients with advanced esophagogastric cancer
Study Objectives:	This is a phase II study of Nintedanib in patients with metastatic or recurrent esophagogastric cancer. The goal of the study is to evaluate the efficacy of Nintedanib, an orally available triple kinase inhibitor targeting the receptors of the vascular endothelial growth factor (VEGF), platelet derived growth factor (PDGF), and fibroblast growth factor (FGF) receptor pathways.
	The primary endpoint will be to evaluate the 6-month progression-free survival (PFS) of Nintedanib. With a total of 32 patients, we have 89% power to detect an improvement in the 6 month PFS from a historical control of 10% to 28%, with a type I and II error rate of 10%.
Study population:	Patients with metastatic or recurrent esophagogastric adenocarcinoma will be eligible. Patients will be allowed to have up to a maximum of one prior chemotherapy regimen for metastatic disease. Patients are allowed to have a maximum of two prior regimens if they previously received neoadjuvant/adjuvant chemotherapy or chemoradiotherapy for their initial localized disease.
Study design:	Single institution, open label, non-randomized, single arm phase II
Number of patients:	32
Study drugs:	Nintedanib, administered orally
Dose and regimen:	Nintedanib 200mg twice daily administered continuously. Patients will continue on treatment until progression of disease. Each cycle consists of 28 days.

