# 14.0 BIOSTATISTICS

This is a single institution, open-label, non-randomized, single-arm phase II evaluation. The primary objective of this study is to determine the 6 month progression free survival (PFS) for patients with advanced or recurrent EG cancer treated with Nintedanib 200 mg twice per day. PFS is defined in Section 12.2.

We are using 6 month PFS as the primary endpoint in this study of 2nd line treatment for advanced EG cancer. Previous studies have estimated the 6 months to be 4.5% with placebo, 12% with everolimus and 18% for ramucirumab. Based on this information, a 6 month PFS of 10% or less will be considered unacceptable while 28% or more will be considered promising. Using an exact binomial single stage design we require 32 patients to differentiate between 6-month PFS of 10% and 28% with type I and II error rates of 10% each. If 6 or more patients are alive and progression free at 6 months, the regimen is declared promising. With a total of 32 patients, we also have 89% power to detect an improvement in the response rate from 5% to 20% with a one-sided type I error rate of 10%. We assume an accrual rate of 1-2 patients per month for study duration of 18-35 months.

Secondary endpoints involve an assessment of the overall response rate (complete and partial responses), as determined by RECIST criteria. Toxicities will also be assessed and tabulated. Correlative analyses will be exploratory in nature. We will assess the relationship between FGFR amplification (by FISH) and FGFR overexpression (by IHC) with progression free survival using log-rank test. Fisher's exact test will be employed to assess these relationships with response.

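### The protocol summary gives 89% power for the primary endpoint, but the exact design in Section 14 has 91.9%, and 89% conflicts with the 10% type II error in the same sentence

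*Combined protocol and SAP*

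**What the plan says.** Section 1.0 (protocol summary) states the operating characteristics of the primary test in one sentence. For the planned sample of 32 it claims: "we have 89% power to detect an improvement in the 6 month PFS from a historical control of 10% to 28"%. The end of that sentence then adds the error rates: "with a type I and II error rate of 10"%. It names no test method and no decision rule.

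Section 14.0 (Biostatistics) gives the design itself:

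- Null value: "a 6 month PFS of 10% or less will be considered unacceptable".
- Alternative value, from the second half of that sentence: "while 28% or more will be considered promising".
- Method and size: "Using an exact binomial single stage design we require 32 patients to differentiate between 6-month PFS of 10% and 28"%. Each of the two errors is set at 10%.
- Decision rule: "If 6 or more patients are alive and progression free at 6 months, the regimen is declared promising".

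Section 14.0 quotes no power figure for PFS. It uses 89% once, for a different comparison: "we also have 89% power to detect an improvement in the response rate from 5% to 20"%, at a one-sided type I error of 10%. No cut-off is given for that comparison.

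**The concern.** Power is one minus the type II error. If the 10% in the summary sentence is the attained type II error, power should be 90%. If it is an upper limit, power should be at least 90%. A power of 89% fits neither reading.

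The summary is where many readers take the operating characteristics of the primary test from. As printed, it suggests a design that falls just short of its own type II limit. Because the summary omits the cut-off, a reader of that page alone cannot tell which of the two numbers to believe. What is at stake is the correctness of a reported figure. The sample size and the decision rule do not depend on it.

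**Working it through.** **Inputs, all from Section 14.0:** n = 32; null 6-month PFS p0 = 0.10; alternative p1 = 0.28; promising if X ≥ 6, where X is the number alive and progression free at 6 months; exact binomial; limits of 10% on each error.

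**Formula:** X ~ Binomial(32, p). Type I error = P(X ≥ 6 | p0). Power = P(X ≥ 6 | p1) = 1 − P(X ≤ 5 | p1).

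**Step 1. Type I error.** At p = 0.10, the probabilities of 0 to 5 successes are 0.0343, 0.1221, 0.2103, 0.2336, 0.1882 and 0.1171, which sum to 0.9056. Type I error = 1 − 0.9056 = 0.0944, within the 10% limit.

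**Step 2. Power.** At p = 0.28, the probabilities of 0 to 5 successes are 0.00003, 0.00034, 0.00204, 0.00794, 0.02237 and 0.04873, which sum to 0.0814. The type II error is 8.1%, within the 10% limit, and power = 1 − 0.0814 = 0.9186. Section 14's PFS design is thus reproduced. The summary's 89% is not: 91.9 − 89 = 2.9 points.

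**Step 3. Could another exact rule give 89%?**

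| n | Promising if | Type I error | Power at 28% |
|---|---|---|---|
| 32 | 5 or more | 21.1% | 96.7% |
| 32 | 6 or more (plan) | 9.4% | 91.9% |
| 32 | 7 or more | 3.6% | 83.3% |
| 31 | 6 or more | 8.3% | 90.3% |
| 30 | 6 or more | 7.3% | 88.4% |

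No cut-off at 32 gives 89%. Keeping the cut-off of 6 and reducing n passes from 90.3% to 88.4%, and both sections state 32 in any case.

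**Step 4. Could an approximation give 89%?** The one-sample normal approximation, one-sided at 10% (z = 1.2816), is

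power = Φ{[√n(p1 − p0) − z√(p0(1 − p0))] / √(p1(1 − p1))}.

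- Without correction: (1.0182 − 0.3845) / 0.4490 = 1.41, giving 92.1%.
- With a continuity correction, subtracting 0.5/√32 = 0.0884 from the numerator: (1.0182 − 0.0884 − 0.3845) / 0.4490 = 1.21, giving 88.8%.

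The corrected version rounds to 89%. It is not the method that Section 14.0 names, and its type II error of 11.2% would still exceed the 10% printed beside it.

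**Step 5. The other 89%, response rate 5% against 20%.** Exact results at n = 32:

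| Cut-off | Type I error | Power at 20% |
|---|---|---|
| 3 or more | 21.4% | 96.8% |
| 4 or more | 7.4% | 90.7% |
| 5 or more | 2.0% | 79.6% |

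The only one of these that keeps the type I error under 10% with power near 89% is 4 or more, at 90.7%. The continuity-corrected normal approximation gives 88.5%.

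**The case against.** The best defence has three parts.

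First, the governing section is right. Anyone running or analysing the trial works from Section 14.0, where sample size, cut-off and error limits all reproduce. The wrong figure appears only in the summary and drives nothing. This stands, and it is why the point is minor.

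Second, the summary names no method, and one familiar approximation gives 88.8% for PFS and 88.5% for response. A single method would thus explain both 89% figures, making the summary's number an approximation that was never aligned with the exact design. Carry-over from the response-rate sentence is an equally open possibility. The documents settle neither, so no origin should be asserted. Neither explanation rescues the figure: Section 14.0 commits to the exact binomial, and under either account 89% still disagrees with a 10% type II error.

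Third, the clash within the sentence is only one point (89% against 90%) and would mislead few readers. That is fair as to weight. But the correct value, 91.9%, lies on the other side of the plan's own 90% line, so rounding cannot explain the difference.

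It can also be said that the response-rate figure is a separate, secondary matter. That is accepted: 89% is close to the exact 90.7%, and it is raised only as something to check.

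**Conclusion.** The concern holds. For the exact rule in Section 14.0 (6 or more of 32, 10% against 28%), power is 91.9% and type II error 8.1%, against the summary's 89% and its implied 11%. Power is understated by 2.9 percentage points. The design meets both of its 10% limits, with an attained one-sided type I error of 9.4%.

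The result needs no outside assumption, since method, sample size, both rates and the cut-off are stated in Section 14.0. It takes the 10% error rates there as upper limits and all 32 patients as counted in the denominator. The misstatement is conservative and does not affect the sample size, the cut-off or the analysis. Severity is minor and confidence high.

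**What to change.** In Section 1.0, change the power for the 6-month PFS comparison from 89% to 92%. Preferably add that this is the exact binomial power with a one-sided type I error of 9.4%, and that 6 or more of 32 patients alive and progression free at 6 months counts as promising. Removing the power figure and keeping only the two 10% error limits would also resolve the contradiction.

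Optionally, in the same edit, check the 89% for response rate in Section 14.0 and state its cut-off and method. If an exact rule of 4 or more responses in 32 was intended, the figures are a one-sided type I error of 7.4% and power of 90.7%.

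The cost is one figure in the summary. Sample size, cut-off, error limits and analysis do not change.

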# 2.1 OBJECTIVES AND SCIENTIFIC AIMS

#### Primary objective:

To evaluate the 6-month progression-free survival (PFS) of Nintedanib in patients with metastatic or recurrent esophagogastric adenocarcinoma.

#### Secondary objectives:

- 1) To evaluate the objective response rate, defined as both complete response (CR) and partial response (PR), as measured by RECIST response criteria.
- 2) To evaluate the tolerability and incidence adverse event profile of Nintedanib in this patient population.
- 3) To perform an exploratory correlative analysis assessing the relationship of FGFR amplification and overexpression with progression free survival and response.

# 3.0 BACKGROUND AND RATIONALE

#### 3.1 Esophagogastric adenocarcinoma

Globally, esophagogastric cancer is diagnosed in nearly one million individuals each year and is the second most common cause of cancer-related death. In the U.S., the incidence of adenocarcinoma of the distal esophagus, GE junction and gastric cardia has increased 4% to 10% per year among U.S. men since 1976 so that it is now the most common histology Most patients with esophagogastric cancer present with stage IV disease, which is incurable. Despite this, systemic chemotherapy can lead to a decrease in cancer-related symptoms and prolong survival. However, even with treatment, for patients with metastatic or recurrent disease, chemotherapy results in response rates in 20-40% of patients and median survivals of only 8-10 months. There is clearly a need for more specific targeted therapies to improve the current status of systemic treatment beyond conventional chemotherapy.

# 3.2 Second line treatment for esophagogastric cancer

There is no current standard of care for second line therapy. There have been a few recent trials comparing 2nd-line chemotherapy to best supportive care (BSC). Thuss-Patience et al. compared irinotecan to BSC in the first phase III trial of second-line therapy in gastric cancer. The median OS was 4mos with irinotecan compared to 2.4mos in the BSC arm (HR 0.46, p=0.012) With irinotecan treatment, there was a median PFS of 2.5 mos (95% Cl 1.6- 3.9mo). In a large Korean trial, Kang et al. compared second-line docetaxel or irinotecan vs BSC and showed improved OS with chemotherapy 5.3 mos vs 3.8mos with BSC (HR 0.66, p=0.07); there was no survival difference between docetaxel and irinotecan. Another trial by

Ueda et al compared irinotecan vs weekly paclitaxel in Japanese patients who were refractory to first-line 5FU/platinum. There was no OS or PFS difference between the two chemotherapy agents. Median OS was 8.4mo with irinotecan, 9.5mos with paclitaxel (HR1.13, p=0.38). The median PFS for irinotecan was 2.3 mos and 3.6 mos for paclitaxel. (HR1.14, p=0.33). In this trial the estimated 6 month PFS was 16% with irinotecan and 14.8% with paclitaxel. These trials have established a benefit of 2nd line chemotherapy in advanced gastric cancer compared to BSC alone.

There have been two large trials evaluating targeted agents in the second line setting. The phase III GRANITE-1 trial of everolimus, an mTOR inhibitor, showed a median PFS of 1.68 mos compared to 1.41 mos in the placebo arm in patients who progressed after first or second line chemotherapy. The 6 month PFS in the everolimus group was 12% compared to 4.3% in the placebo arm. This trial has not met its primary endpoint for survival and is not an FDA approved drug in this population. The phase III REGARD trial of ramucirumab compared to placebo in patients who progressed on first line therapy showed an overall survival benefit of 1.3 months compared to placebo.  In the study, the ramucirumab arm had a median PFS of 2.1 mos vs 1.3 mos with placebo. In this study, the estimated 6 month PFS was 18 months for ramucirumab compared to 4.5 months with placebo.

Based on the studies referenced above, we now have data that 2nd line conventional chemotherapy is beneficial compared to best supportive care alone. The REGARD study showed the 6 month PFS with placebo was 4.5% and with ramucirumab 18%. There is an unmet need in patients with metastatic and recurrent EG cancer to discover new novel agents.

# 3.3 Vascular endothelial growth factor (VEGF) and anti-angiogenic therapy

Angiogenesis is involved in tumor growth and development of metastases. Weidner et al. showed a statistically significant correlation between the density of microvessels in histologic specimens of human breast cancer and clinical outcomes, including the incidence of metastases, as well as overall and relapse-free survival.

Of the identified angiogenic growth factors, Vascular Endothelial Growth Factor (VEGF) and its high affinity receptor VEGFR-2 have been identified as crucial regulators of both normal and pathologic angiogenesis. VEGF produces a number of biologic effects, including endothelial cell mitogenesis and migration, and induction of proteinases, leading to remodeling of the extracellular matrix, increased vascular permeability, and maintenance of survival for newly formed blood vessels. Increased expression of VEGF has been measured in most solid tumors, including tumors of the lung, breast, thyroid, gastrointestinal tract, kidney, bladder, ovary, as well as angiosarcomas.

Suppression of neo-angiogenesis via inhibition of VEGFR-2 is a promising strategy for the treatment of solid cancers. Bevacizumab, a chimeric murine monoclonal antibody against VEGF, has been extensively studied in a number of solid tumor malignancies. The addition of bevacizumab to cytotoxic chemotherapy has been shown in several phase III clinical trials to increase the efficacy of chemotherapy. Most recently, data was presented

showing bevacizumab leading to an improvement in overall survival in cervical cancer and previous studies have shown benefits in progression free survival in colorectal cancer, lung cancer, and breast cancer.

#### 3.4 Angiogenesis in esophagogastric cancer

A number of studies have evaluated the role of the VEGF pathway in esophageal cancer as a prognostic marker and indicate the expression of VEGF in tumors correlates with more advanced tumor stage, the presence of nodal and distant metastasis, and with a poorer survival outcome. In esophageal adenocarcinoma, increasing VEGF expression correlates with the transition from Barrett's esophagus to high grade dysplasia, and with the transition from microinvasive to locally advanced cancer. These pre-clinical data suggest that angiogenesis is a viable target for therapy in advanced esophagogastric cancer.

Our group has previously performed a multicenter phase II evaluation of bevacizumab and cisplatin/irinotecan in patients with advanced gastric and GE junction adenocarcinoma. The addition of bevacizumab to cytotoxic chemotherapy significantly improve the time-to-progression (8.3 months; 95% CI, 5.5 to 9.9 months) and overall survival (12.3 months; 95% CI, 11.3 to 17.2 months) of patients compared to the historical time-to-progression of 5 months. Therapy was well tolerated, although a 6% incidence of gastric perforation or near-perforation and a 2% incidence of myocardial infarction were noted.

In the phase III REGARD trial, ramucirumab, a monoclonal antibody VEGFR-2 antagonist prolonged survival in patients with advanced gastric cancer. Ramucirumab in patients who progressed on first line therapy showed an overall survival benefit compared to placebo. FDA granted ramucirumab priority review for advanced gastric cancer. These results validate the role of VEGFR-2 signalling as an important therapeutic target in advanced gastric and esophageal adenocarcinoma.

#### 3.5 MSKCC Clinical data of multi-kinase inhibition in esophagogastric cancer

There is clear clinical rationale to study more than one pathway in esophagogastric cancer, as indicated by our recently completed MSKCC initiated phase II study of single agent Sorafenib in patients with metastatic esophagogastric cancer (IRB 09-016, Proc ASCO 2013 Ku et al). Sorafenib is an oral multi-kinase inhibitor with activity against VEGFR, platelet-derived growth factor receptor (PDGFR), as well as against the serine/threonine kinases Raf-1.

In our study of Sorafenib in 2nd/3rd line setting in patients with metastatic esophagogastric cancer, we met the primary endpoint of improving 2-month progression-free survival. The median PFS was 3.6 mos (95% CI 1.8 to 3.9 mos) with a median overall survival of 8.8 mos (95% CI, 5.9 to 11.1 months). An ongoing complete response (44+ months) was observed in a patient with Stage IV esophageal adenocarcinoma with biopsy proven metastatic neck lymphadenopathy who developed recurrence after prior chemoradiotherapy and surgery. This patient continues to maintain a complete response. A second patient with gastroesophageal junction adenocarcinoma had protracted stable

disease in bulky celiac node disease (26+ months). The majority of tumors tested positive for phospho-ERK by immunohistochemistry (26/32, 82%). Twenty of the 34 evaluable patients (59%) were progression free at 2 months (p=0.08); with the pre-specified Type I and II error rates of 10% and historical 2-month PFS of 50% without treatment, this regimen shows promise and activity in gastroesophageal cancers.

# 3.6 Targeting multiple relevant pathways in esophagogastric cancer

Preclinical animal models suggest that targeting VEGF-VEGFR signaling is beneficial at the start of treatment, but with continued drug treatment and under pressure of the VEGF blockade, other signaling molecules provide alternate mechanisms to drive disease progression. Among the potential compensatory mechanisms include upregulation of the platelet-derived growth factor (PDGF) and fibroblast growth factor (FGR) pathways. The PDGF receptor (PDGFR) has a role in promoting angiogenesis, tumor growth and metastasis by regulating the migration and adherence of pericytes and smooth muscles cells to endothelial cells. The FGF receptor (FGFR) has been described as a potential escape mechanism with tumor cells switching from VEGF to FGF signaling to attract endothelial cells.

# 3.7 FGFR2 in gastric cancer

The family of fibroblast growth factors (FGFs) and FGF receptors (FGFRs) plays a critical role in cell behaviors, such as proliferation, differentiation, migration and survival, and are fundamental to embryonic development, regulation of angiogenesis, and skeletal development. The FGFR ligands belong to the FGF family comprising of 18 secreted ligands-induced dimerization and bind to adapter proteins. Subsequent downstream signaling occurs through two main pathways via the intracellular receptor substrates FGFR substrate 2 and phospholipase C $\gamma$  (PLC $\gamma$ ), leading ultimately to upregulation of the Ras-dependent mitogen-activated protein kinase (MAPK) and Ras-independent phosphoinositide 3-kinase (PI3K)-Akt signaling pathways).

Activation of FGFRs as a result of amplification, mutation or translocation of FGFR genes or over-expression of FGFR proteins or overproduction of FGF ligands has been shown to be oncogenic. Inhibition of FGFR11may have clinical utility in cancers that overexpress FGFRs, such as breast, esophageal, bladder, gastric, and lung cancers, or display a prevalence of FGFR mutations, such as inbladder cancer.

FGFR gene amplification often leads to FGFR overexpression, which can provoke ligandindependent signaling. FGFR2 amplifications have been reported in up to 7% of gastric cancers, most of which are diffuse-type with relatively poor prognosis. The presence of FGFR2 gene amplifications in gastric cancer is associated with sensitivity to inhibition of FGFR signaling by tyrosine kinase inhibitors and monoclonal antibodies in preclinical models. The frequency of FGFR1 and FGFR2 overexpression is significantly larger than the frequency of amplification in gastric cancers, which is reported up to 41%, indicating that gene amplification is not the sole mechanism leading to receptor overexpression. FGFR2 and PDGFR expression in esophageal and gastric cancers have also been shown to

be associated with high metastatic potential, aggressive tumor biology, and poor outcomes.  $^{\scriptscriptstyle 31,39}$ 

Inhibition of FGFR2 in gastric cancers using a novel multi-kinase that specifically targets FGFR may provide more potent inhibition of the oncogenic pathways and result in improved therapeutic efficacy than seen with other tyrosine kinase inhibitors. Nintedanib with its favorable toxicity profile and multi-kinase targets may make this agent a promising agent and further development of this agent in esophagogastric malignancies is clearly indicated.

#### 3.8 Nintedanib

#### 3.8.1 Pre-clinical rationale

Nintedanib is an orally available potent small molecule triple kinase inhibitor inhibiting VEGFR 1-3, FGFR 1-3 as well as PDGF receptor  $\alpha$  and  $\beta$  in the low nanomolar range. VEGFR-2 is considered the crucial receptor involved in initiation of the formation as well as the maintenance of tumor vasculature.

In vivo experiments demonstrated good anti-tumor efficacy at doses of 50 – 100 mg Nintedanib, leading to a substantial delay of tumor growth or even complete tumor stasis in xenografts of a broad range of differing human tumor types. Furthermore, established xenograft tumors rapidly responded to treatment with Nintedanib. Histological examination of treated tumors showed a marked reduction of tumor vessel density by approximately 80%. In addition preclinical models show that Nintedanib may have a direct anti-tumour effect on those malignant cells which overexpress PDGFR and/or FGFR (e.g. H1703 NSCLC cells).

